CLINICAL TRIAL PROTOCOL

**Intrafractional 6D head movement during stereotactic intracranial
radiation therapy with thermoplastic mask fixation**

A prospective observational study

Version: 1.0

Date: 25.01.2019

Principal Investigator

Ao.Univ.[name]. [name]
Universitätsklinik für Strahlentherapie-Radioonkologie
Medizinische Universität Innsbruck
[name]
[name]

Sponsor

Medical University Innsbruck
[name]
[name]
[name]

1. Study Summary

Title	Intrafractional 6D head movement during stereotactic intracranial radiation therapy with thermoplastic mask fixation
Study Center	single center Department of Therapeutic Radiology and Oncology Innsbruck
Study Design /Methodology	A prospective observational study
Objectives	to investigate intrafractional head motion during stereotactic intracranial radiation therapy with non invasive thermoplastic mask fixation with repeated X-ray position verification during RT sessions.
Endpoints	3D deviation of head position, rotational and translational deviations. Development of head deviation with time during single RT sessions
Number of Subjects	5
Eligibility Criteria	Male and female patients with a single intracranial solid tumour. Stereotactic radiation therapy with immobilization by non invasive thermoplastic mask.
Study Interventions and Measures	repeated X-ray position verification during RT sessions
Statistical Methodology	calculation of 3D deviation from X, Y, Z translational deviation. Descriptive statistics of 3D, translational and rotational deviation. Analysis of time dependent deviation with Spearman's correlation. ANOVA Analysis of deviations in 2-minute interval groups.

2. Introduction

2.1. Study Rationale

Invasive head fixation by means of a stereotactic ring for stereotactic intracranial radiation therapy has largely been replaced by non-invasive thermoplastic mask fixation. While the deviation between RT sessions can be minimized using modern image-guided radiation therapy, the role of intrafractional head movement and its effect on treatment accuracy is still debated. Previous studies have attempted to estimate intrafractional deviation by performing position measurements at the beginning and the end of RT sessions. However, this method is not accurate enough to map patient motions during a treatment session.

2.2. Background and scientific bases

In recent years advances in non-invasive patient immobilization as well as in image-guided radiation therapy (IGRT) have enabled the use of thermoplastic masks and hypofractionated radiotherapy for single brain metastases (1). The use of a rigid, invasive stereotactic head-ring provides reliable and precise immobilization for single fraction radiosurgery. The ring is securely mounted to the skull using pins or screws, thereby achieving a setup inaccuracy of less than 1 mm (2, 3). However, this method suffers from disadvantages such as the need to surgically implant the ring. It also entails the risk of bleeding and infection, possibly accompanied by pain and generally by patient discomfort. Ring implantation, planning and irradiation have to be performed on the same day, which can put a significant burden on clinical and organisational resources. Moreover, this prohibits the use of fractionated RT. The use of non-invasive thermoplastic masks together with image guidance can minimise these limitations and has currently replaced invasive immobilization. (2, 4)

Several studies have shown that image guidance makes set-up and repositioning uncertainty with the non-invasive mask immobilization comparable to that of invasive stereotactic ring application (2, 3, 5, 6). Nevertheless, this method may have less intrafractional accuracy due to the non-rigid construction and indirect immobilization of the skull. This uncertainty can be caused by patient movements during individual radiotherapy sessions. Many studies reported this effect only by means of quantifying pre- and postfractional deviations of the patient's head by either CBCT (cone beam computed tomography) or ExacTrac (2, 3, 7, 8). However, real intrafractional movements cannot be mapped by measuring the position of the head only at the beginning and the end of treatment since this gives no information on possible head movements during the individual irradiation treatments, which last up to 20 minutes each. Larger deviations would need to be accounted for by increasing the PTV margins, thereby exponentially increasing the irradiated volume. Studies have shown that the risk of complications, such as radionecrosis, directly correlates with the size of the irradiated PTV (9, 10).

2.3. Study objectives

The purpose of the present study is to evaluate the precision and reliability of mask fixation of the head during the entire duration of stereotactic RT sessions. In order to assess position accuracy not only at the beginning and the end of the sessions, we repeatedly map deviations of the head position in both translation and rotation, by concomitantly measuring intrafractional movement using the ExacTrac 6D X-Ray Positioning System (Brainlab AG, Munich, Germany). From the obtained data we evaluate the need to adjust safety margins around the gross tumor volume (GTV) whenever the investigated thermoplastic mask is used instead of invasive ring fixation.

3. Study design and Methods

3.1. General study design

This is a prospective observational study investigating patient motion during radiation therapy sessions of patients treated with stereotactic radiation therapy.

3.2. Study population

5 patients treated with intracranial stereotactic radiation therapy for single primary tumours at the Department of Therapeutic Radiology and Oncology Innsbruck.

3.2.1. Inclusion criteria

- Males and females ages ≥ 18
- Single intracranial primary tumour or metastasis
- conventional or hypofractionated stereotactic radiation therapy
- position verification with ExacTrac 6D X-Ray Positioning System
- Karnovski performance scale 80 or higher

3.2.2. Exclusion criteria

- Position verification with ExacTrac 6D X-Ray Positioning System not possible if the mask frame overlaps the orthogonal KV X-ray images used for position measurement.

3.3. Study procedures

3.3.1. Date range of the study

Enrolment of patients between November 2014 and September 2015

3.3.2. Procedures

To detect intrafractional motion during treatment delivery, the ExacTrac in-room based monitoring system (Brainlab AG, Munich, Germany) is used (11, 12). It is employed in this study to repeatedly record 3D deviations of the target isocenter for both translation and rotation, during a single RT session.

Following thermoplastic mask molding, contrast-enhanced treatment planning CT is performed. CT scans are also used for image registration to reference ExacTrac recordings and CBCT-guided patient positioning at the beginning of each treatment session. Calculated 6D shifts are checked and, if indicated, translational and rotational deviations from reference positions are computed and corrected by adjusting the treatment couch (equipped with the HexaPod evo RT system, Elekta AB, Stockholm, Sweden) until translational deviation in each direction are < 1.0 mm and rotational errors are $< 1.0^\circ$.

The first ExacTrac measurement is taken before treatment start at a rotatable baseplate position of 0° . This initial ExacTrac recording is used as a reference point for comparison with the subsequent intrafractional measurements made during irradiation ($N = 3$ to 10). Patient positions are not corrected during a treatment session.

ExacTrac measurements are taken simultaneously with arc irradiations (five per RT session) at gantry angles of 0° , 90° , 180° or 270° with a tolerance range of $\pm 10^\circ$. For shaped beam application, ExacTrac recordings are taken immediately after each field application (five to eight per fraction). A final pair of ExacTrac images at a reset baseplate position of 0° are acquired at the end of each treatment session.

4. Data management

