4.1.2. Data collection and variable abstraction

The following parameters are extracted, saved in a database and analysed:

- baseplate position [$^\circ$]
- elapsed time since treatment start
- X axis translation
- Y axis translation
- Z axis translation

- X axis rotation
- Y axis rotation
- Z axis rotation
- 3D deviation is calculated from X-, Y- and Z-translation

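### Pooling all sessions, patients and both delivery techniques on one time axis can make a change in which sessions contribute look like head drift, or hide real drift

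*Combined protocol and SAP*

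**What the plan says.** The Study Summary names the development of deviation over the course of a single session as an endpoint. Its statistical methodology includes "ANOVA Analysis of deviations in 2-minute interval groups". Section 5 adds one Spearman correlation between 3DV and time, and says only that an ANOVA takes this further. Neither place mentions patient, session or technique.

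Section 3.3.2 gives two imaging schedules. For arcs, "ExacTrac measurements are taken simultaneously with arc irradiations (five per RT session". For the other technique, "For shaped beam application, ExacTrac recordings are taken immediately after each field application (five to eight per fraction". Both end alike: "A final pair of ExacTrac images at a reset baseplate position of 0° are acquired at the end of each treatment session". The number of images after the reference is given by "comparison with the subsequent intrafractional measurements made during irradiation ($N = 3$ to 10".

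On duration, section 2.2 speaks of "individual irradiation treatments, which last up to 20 minutes each". No typical length is given, and none by technique.

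The extraction list in section 4.1.2 has baseplate position, "elapsed time since treatment start", three translations, three rotations and the 3D deviation. It has no patient or session identifier, no technique and no session duration.

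**The concern.** The endpoint is about change within a session. A pooled correlation or a one-way ANOVA on time intervals compares whatever images fall early with whatever images fall late. When session lengths differ, these come from different sets of sessions: every session supplies early images, and only long ones supply late images. If sessions that run long also have a different level of motion, because of the technique or because of the patient, the interval means change along the axis even when no head drifts. The distortion is in the means themselves, not only in the p values, and it can go either way.

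At stake is whether the study can say that deviation grows with time on the table. With no technique, session or duration field in the planned dataset, nobody could check afterwards whether an observed trend was movement or composition.

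**Working it through.** The plan gives no figure for this point, so there is none to reproduce. The inputs from the documents are 5 patients, sessions of up to 20 minutes, 3 to 10 images after the reference, 2-minute groups and two imaging schedules. Durations by technique, sessions per patient and motion levels are not given; the values below are assumptions.

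**1. Windows against images.** Mean spacing = session length / number of images.
- At 20 minutes there are 20/2 = 10 windows. Spacing is 20/3 = 6.7, 20/6 = 3.3, 20/9 = 2.2 and 20/10 = 2.0 min. With 6 images at least 10 − 6 = 4 windows are empty for that session; with 9, at least 1.
- At 10 minutes there are 5 windows. Spacing is 10/5 = 2.0, 10/6 = 1.67 and 10/8 = 1.25 min, so with 5 or more images the windows are not narrower than the mean spacing.

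Empty windows are therefore certain only in sessions where images are fewer than windows, as near 20 minutes with fewer than 10 images. An empty window does not in itself bias a mean.

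**2. Composition effect by hand, no drift.** Assume 3 arc patients (10-minute sessions, 6 images) and 2 shaped-beam patients (20-minute sessions, 8 images), 6 sessions each. Motion is normal with SD 0.35 mm per axis for arcs and r times that for shaped beams. The reference image is left out.
- Mean 3DV for arcs = 2 × 0.35 × √(2/π) = 0.559 mm; for shaped beams 0.559 × r.
- Before 4 minutes: arc images at 1.67 and 3.33 min give 3 × 6 × 2 = 36; shaped-beam images at 2.5 min give 2 × 6 × 1 = 12. The mix is 75% to 25%, so the early mean = 0.559 × (0.75 + 0.25r).
- After 11 minutes only the 20-minute sessions remain, so the late mean = 0.559 × r.

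| r | early mean (mm) | late mean (mm) | pooled Spearman rho (simulated) |
|---|---|---|---|
| 0.67 | 0.51 | 0.37 | −0.19 |
| 1 | 0.56 | 0.56 | about 0 |
| 1.25 | 0.59 | 0.70 | 0.11 |
| 1.5 | 0.63 | 0.84 | 0.19 |
| 2 | 0.70 | 1.12 | 0.29 |

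With equal session lengths rho is again about 0. At r = 0.67 the composition pulls the late mean down by 0.51 − 0.37 = 0.14 mm, enough to cancel a real rise of that size.

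**3. Simulation with variable lengths, no drift.** There were 1000 runs per row and 5 patients. In the mixed rows, 1 to 4 patients have longer sessions (14–20 min, 6–9 images) and the rest shorter ones (7–12 min, 6 images). Each patient has 10 sessions unless stated. Clustering means patient and session log-SDs of 0.3. Slopes are per session, averaged per patient, then tested with a t test on 5 values.

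| Setting | ANOVA rejects | Spearman rejects | Slopes reject | First to last interval mean (mm) |
|---|---|---|---|---|
| all sessions 20 min, no clustering | 4.4% | 4.9% | 6.1% | 0.56 to 0.56 |
| two lengths, equal motion, no clustering | 3.8% | 4.5% | 3.8% | 0.56 to 0.56 |
| two lengths, equal average motion, clustering | 11.1% | 25.0% | 3.5% | 0.61 to 0.62 |
| longer sessions 1.3×, no clustering | 30.6% | 36.1% | 4.9% | 0.63 to 0.72 |
| longer sessions 1.3×, clustering | 19.8% | 34.1% | 4.6% | 0.68 to 0.79 |
| same, 5 sessions per patient | 10.5% | 21.4% | 4.3% | 0.69 to 0.79 |
| longer sessions 0.7×, clustering | 19.9% | 44.1% | 3.3% | 0.54 to 0.42 |

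In the mixed settings the share of sessions contributing to an interval falls from about 0.9 at the start to 0.22 at 16–18 min and 0.10 at 18–20 min. In the third row the techniques do not differ on average. The excess rejections arise because session length belongs to the patient and patients differ in level.

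**The case against.** **The artefact needs conditions the documents do not establish.** This stands. Motion must differ between long and short sessions; with equal lengths, or with equal motion and no clustering, nothing happens. Neither durations by technique nor motion levels are given. A reader might infer that the late-versus-early comparison is in fact a comparison of shaped beams with arcs. The hand calculation makes it so by construction, but the documents do not say that either technique runs longer.

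**The interval width is not at fault.** This stands too. A reader might infer that 2-minute groups are finer than the imaging schedule. That is so near 20 minutes with fewer than 10 images, but 20 minutes is an upper limit, and in 10-minute sessions with 5 or more images it is not so. The Spearman correlation uses no windows and shows the same artefact, so wider windows would not cure it.

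**The consequence is limited.** The only stated decision rule, in section 6, concerns motion above 1 mm and not a trend. In the hand calculation the late mean passes 1 mm only at r = 2, and there the longer sessions really do have that level; only its reading as drift would be false. This limits the harm but does not remove it, because development over time is itself an endpoint.

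**Duration, and perhaps identity, can be recovered.** The final image dates the end of each session, and section 4.1.3 mentions patient identifiers in a separate file. That makes the repair cheap. It does not put these terms into the analysis.

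It might also be argued that images during and just after the beam answer different questions. The documents give no evidence that the readings differ, so no weight is placed on this beyond keeping the techniques visible.

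**Conclusion.** The point holds in conditional form. As written, the time analysis cannot separate movement within sessions from a change in which sessions contribute, because it pools sessions of unequal length, both techniques and all patients, with no term for any of them. Under the assumptions shown, a study without drift would give a significant pooled ANOVA in 10.5% to 30.6% of runs and a significant Spearman correlation in 21% to 44% once patients or techniques differ in motion. The false change in the mean is about 0.1 mm at motion ratios of 0.7 or 1.3, and larger at the assumed ratio of 2. It can be a rise or a fall. The real size and direction cannot be derived from the documents, and it would be wrong to say that the study's trend will be false. It is a change that should be made, because the remedy is inexpensive and, in these simulations, brings the error rate back to 3.3% to 6.1%.

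**What to change.** - **Section 4.1.2:** add a coded patient and session identifier, delivery technique (arc or shaped beam) and session duration. All can be read from existing records.
- **Section 5:** base the time conclusion on change within sessions, for example a slope of 3DV on time for each session, averaged per patient and tested across the 5 patients. Leave out the reference image, whose deviation is zero by definition. This replaces the p values of the pooled Spearman correlation and the one-way ANOVA.
- **Interval means:** keep them as description, shown by technique with the number of patients and sessions in each interval. Draw no conclusion about drift from intervals that not all sessions reach.
- **Clock:** state one time zero. Section 4.1.2 counts from treatment start and section 5 from the first image, which precedes it. The difference moves images between intervals, although a constant shift within a session leaves its slope unchanged.

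The cost is a few fields and some more analysis, with no new imaging. The downside is wider uncertainty: the test rests on 5 values (5 − 1 = 4 degrees of freedom), and slopes from sessions with only 3 images will be imprecise.

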4.1.1. Data sources

Patient head position data is extracted from the ExacTrac 6D X-Ray Positioning System.

4.1.2. Data collection and variable abstraction

The following parameters are extracted, saved in a database and analysed:

- baseplate position [$^\circ$]
- elapsed time since treatment start
- X axis translation
- Y axis translation
- Z axis translation

- X axis rotation
- Y axis rotation
- Z axis rotation
- 3D deviation is calculated from X-, Y- and Z-translation

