4.1.3. Data capture methods and storage

All data collected is be saved databases using Microsoft Excel and IBM SPSS Statistics. The files are be stored encrypted on our department's file servers. Patient identifiers are stored in a separate file. All data and records generated throughout the course of the study are kept confidential. Only the study investigators have access to the data. In case of publication of the studies results patients personal information will be kept confidential.

5. Statistical analysis

Translations in the x (medial-lateral), y (superior-inferior) and z (anterior-posterior) directions as well as rotations around the x (transversal), y (longitudinal) and z (sagittal) axes are analysed. The resulting 3DV is calculated as follows:

$$3DV = \sqrt{x^2 + y^2 + z^2}$$

IBM SPSS Statistics 22 (IBM Cooperation, Armonk, NY, USA) is used for statistical analysis To evaluate the correlation between the time elapsed since the first measurement in each treatment session and the 3DV, Spearman's rank correlation coefficient is calculated. An analysis of variance (ANOVA) is used to analyse this correlation further. A p value of < 0.05 is deemed to be significant.

6. Ethical considerations

The study is conducted in accordance with the ethical standards of the 1964 Helsinki Declaration and its later amendments. There is no risk involved for the participating patients. All parameters and measurements required for the study are routinely collected as part of the treatment. All patient data is kept confidential and the rights and welfare of the enrolled patients is not adversely affected. Every patient is informed about the analysis of data collected over the course of the treatment. Written informed consent for this analysis is obtained. While there is no direct benefit for the patients participating in the study, results from the study will help improve treatment for future patients treated in our department. Information about the accuracy of treatment and the extent of patient motion during treatment sessions is vital in order to determine the necessary safety margins used in

treatment planning. If patient motion is found to significantly exceed 1 mm an additional safety margin will be implemented.

7. Literature

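### Do the two definitions of elapsed time, and the zero reading of the reference image, distort the time-trend analysis?

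*Combined protocol and SAP*

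**What the plan says.** - **Time to be extracted.** Section 4.1.2 lists "elapsed time since treatment start", alongside the baseplate position and the six translations and rotations.
- **Time to be analysed.** Section 5 relates "the time elapsed since the first measurement in each treatment session and the 3DV" and says that "Spearman's rank correlation coefficient is calculated". An ANOVA is to take this further. The Study Summary describes it as "ANOVA Analysis of deviations in 2-minute interval groups". The threshold is given as "A p value of < 0.05 is deemed to be significant".
- **When the first image is taken.** Section 3.3.2: "The first ExacTrac measurement is taken before treatment start".
- **What the first image is for.** Same section: "This initial ExacTrac recording is used as a reference point for comparison with the subsequent intrafractional measurements made during irradiation". The number 3 to 10 follows directly and belongs to those later measurements.

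The plan gives no conversion between the two clocks, no start point for the first 2-minute group, and no explicit rule on whether the reference image enters the correlation, the ANOVA or the descriptive statistics.

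**The concern.** How head deviation develops during a session is a named endpoint, and both planned time analyses rest on one time variable that the plan defines in two ways. The clocks differ by the gap between the first image and the start of treatment. That gap is not in the extraction list and may vary between sessions, so images could fall into different 2-minute groups depending on the clock used.

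The second worry is larger. On the Section 5 clock the reference image sits at time zero. If deviations are measured from that image, its 3DV is zero by definition. One such point per session, pooled with the rest, would pull the low end of the time axis down to zero and produce a positive correlation in patients who do not drift at all. The results are meant to inform safety margins, so an artificial trend would matter.

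**Working it through.** The plan states no expected correlation or power, so there is no figure of its own to reproduce. The two issues are checked separately.

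**Inputs from the protocol:** 3 to 10 later images per session and 3DV as the root of the summed squared translations (Sections 3.3.2 and 5); sessions of up to 20 minutes (Section 2.2); 5 patients; significance at 0.05.

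**Assumed, because not given:** the gap between first image and treatment start, the number of sessions, the drift and the measurement error. Errors are taken as independent between images.

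**1. The clock alone, reference image left out**

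*Within a session.* Adding a constant to every time leaves the ranks unchanged, so Spearman's rho is identical.

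*Pooled over sessions.* With gaps of 0.5 to 3 minutes, 50 sessions of 8 to 20 minutes and error SD 0.3 mm per axis, mean rho was:

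| Drift (mm/min) | Time from first image | Time from treatment start | Difference |
|---|---|---|---|
| 0.02 | 0.103 | 0.104 | under 0.001 |
| 0.05 | 0.422 | 0.415 | 0.007 |
| 0.10 | 0.755 | 0.743 | 0.012 |

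*Group membership.* In a full 2-minute group, a gap of g minutes (up to 2) moves a share g/2 of the images into the next group. For gaps uniform on 0 to 2 minutes the mean is 1/2. Simulation with image times uniform over 0 to 15 minutes gives 48%, slightly less because the last group is incomplete. For gaps of 1 to 4 minutes it gives 91%, with a mean shift of about 1.2 groups.

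*ANOVA result.* Many images are relabelled, but the groups remain consecutive 2-minute slices of the session with the cut points displaced. Rejection rates at 0.05 on the two clocks (600 runs, 3 to 10 images per session, error SD 0.3 mm) were:

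| Setting | Gap 0–2 min | Gap 1–4 min |
|---|---|---|
| No drift, 50 sessions | 0.055 and 0.058 | 0.047 and 0.038 |
| 0.02 mm/min, 50 sessions | 0.298 and 0.305 | 0.398 and 0.392 |
| 0.05 mm/min, 10 sessions | 0.823 and 0.798 | 0.868 and 0.872 |

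The largest difference is 0.823 − 0.798 = 0.025. The simulation error of one such rate is about √(0.8 × 0.2 / 600) = 0.016, so the differences are of the order of that error.

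**2. The reference image, if it were kept as an observation**

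Let k be the number of later images and p = 1/(k+1) the share of points at (0, 0). On ranks scaled to the interval 0 to 1, the tied points lie at p/2 and the others are uniform on p to 1, independent in time and 3DV when there is no trend. Then:

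- covariance = p(1−p)²/4 + (1−p)p²/4 = p(1−p)/4
- variance = p(1−p)/4 + (1−p)³/12
- rho = 3p / (3p + (1−p)²) = 3p / (1 + p + p²)

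| k | p | rho with no trend |
|---|---|---|
| 3 | 1/4 | 0.75 / 1.3125 = 0.57 |
| 6 | 1/7 | 0.4286 / 1.1633 = 0.37 |
| 10 | 1/11 | 0.2727 / 1.0992 = 0.25 |

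Simulation with no trend (error SD 0.4 mm, 500 runs per setting) agrees. With 5 sessions, Spearman rejects in 43 to 87% of runs and the ANOVA in 81 to 86%. With 25 or more sessions both reject in at least 99.8%. With the reference image left out, mean rho is about 0 and rejection is about 3 to 7%.

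**3. Which of these does the plan describe?**

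Section 3.3.2 gives the initial image one role, that of the comparator, and counts as intrafractional measurements only the images that follow it. Section 5 uses the first image to set the zero of the time axis. Neither section lists it as a deviation to be analysed. The natural dataset is 3 to 10 deviations per session, which is the case with no artefact.

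**The case for a change.** The strongest case for a change is that the artefact, if it occurred, would decide the conclusion. Under an assumed real drift of 0.02 mm/min it would lift rho from 0.10 to 0.42, and with no drift at all it would make a significant result nearly certain once there are 25 sessions. Section 5 starts its clock at the first measurement, so a row at time zero could easily appear in the data file. No analysis rule excludes it, and a sentence would do so.

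The size of the effect stands, and so does the absence of an explicit rule. The probability of the error is the weak part. It requires an analyst to treat as a measured movement an image that Section 3.3.2 defines as the zero point. The zero is itself an inference: Sections 4.1.2 and 5 do not say that x, y and z are differences from the first image. If they were residuals from the planning CT, which Section 3.3.2 allows to be just under 1.0 mm in each direction after correction, the first reading would generally not be zero and this artefact would not arise in that form.

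It is also fair to say that the Section 5 clock cannot be derived with certainty from the listed variables. However, the list reads as one record per measurement. If the first image has a record, its own (negative) time from treatment start supplies the gap by subtraction. Enrolment is dated November 2014 to September 2015 and the protocol January 2019, so a new extraction rule would depend on what the existing records hold.

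**Conclusion.** The mismatch between Sections 4.1.2 and 5 is real, but it is a matter of wording. With the reference image left out, the choice of clock changes rho by about 0.01 (0.012 at the steepest drift examined) and ANOVA rejection by a few percentage points at most. The regrouping of 48% or 91% of images describes displaced cut points and does not measure error in the conclusion.

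The damaging scenario, a rho of 0.25 to 0.57 with no trend, depends on a step the plan does not direct and that Section 3.3.2 argues against. Read naturally, the plan gives sound time-trend results on this point, and the missing detail is one that analysts would fill sensibly.

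This rests on assumed gaps of up to 4 minutes, assumed drifts of up to 0.10 mm/min and errors independent between images. The range 0.25 to 0.57 needs only the number of later images and the absence of a trend. Repeated images within 5 patients are a separate question, not assessed here.
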